#### 9. STATISTICAL ANALYSIS

The similarity of data derived from the App and video will be compared to establish the respective value of these sources of data. Parental counts (via telephone App) and video recordings of number of spontaneous requests used by the child will be analysed using intention-to-treat approach in a mixed ANOVA model, accounting for clustering within school and covarying for baseline score on the same measure. This will inform the sample size for a possible full randomised control trial. A preliminary power calculation (2-tailed p=.05 and assuming 10% drop-out or failure of equipment) indicates that the study has 47% power, for an effect size of 0.5 and 62% power for an effect size of 0.6 on the secondary measure of rate of spontaneous requests using PECS. Change in vocabulary use (assessed by the CDI) will also be compared across groups. In addition we will explore the impact on outcome of child characteristics e.g. age, developmental level and parental fidelity to treatment as rated by the therapist (see measures).

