## **5.2 PARTICIPANTS**

The present feasibility study will focus on young children (between 2 and 10 years of age) since our aim is to explore the possibility of establishing strong independent and functional communication skills as early as possible. A total of 64 young children (N=64) will be recruited in the study.

Inclusion criteria:

- Child: age between 2 and 10 years
- Clinical diagnosis of autism spectrum disorder and meeting cut-off for autism symptoms (i.e. ≥15 on the Social Communication Questionnaire)
- Non/minimally verbal (i.e. fewer than 10 words used on a regular basis)
- Parents willing to consent to participation and able to engage in intervention at home.

*Exclusion criteria*: Children who have more than 10 words used regularly; have severe visual impairment; have a twin brother or sister. Parents with reduced levels of spoken and/or understanding of English, which would limit participation.

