## 6. ASSESSMENTS (see table below for details of time points for assessment)

## 6.1. Child characteristics

The following measures, selected to assess children's characteristics, are all widely used in the autism field and are of established reliability and validity.

*i) Autism symptoms:* The Social Communication Questionnaire - Lifetime version  is a brief parent/caretaker questionnaire that assesses the presence of autism symptoms *ii) Developmental level*: The Mullen Scales of Early Learning (MSEL)  provide a comprehensive standardised measure of motor, perceptual, and language abilities in children aged from birth to 68 months. Raw scores on each subscale will be transformed to age-normed *t*-scores.

*iii) Communication:* Communication Development Inventory  (CDI) Words and Gestures The parent rated version of this questionnaire, designed for typically developing children aged 8-18 months. Raw scores will be used to assess the understanding and use of vocabulary and nonverbal gestural signals. It will also be used at the end of intervention to explore whether there has been any overall change in children's communication skills. *iv) Adaptive Behaviour*: The Adaptive Behaviour Assessment System  (ABAS) which extends from birth to 89 years, is a measure of adaptive skills across 3 major domains: Conceptual, Social, and Practical.

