#### 6. Summary of assessment measures

The following table summarises the measures to be used at baseline, end of treatment and at short term follow-up:

Descriptive measures (baseline only)	Pre and post treatment measures	Post treatment only	Follow-up*
Social Communication Questionnaire	PECS usage (telephone App and video)	Assessment of parent treatment fidelity*	PECS usage* (telephone App and video)
Mullen Scales of Development	Communication Development Inventory (CDI)	Feedback on participation using Social Validity Questionnaire*	
Adaptive Behaviour Assessment System (ABAS)		Child and Adolescent Service Use Schedule (CA- SUS)	

\* treatment group only

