## 8. STUDY OUTCOMES

As this study is designed as a feasibility study primary outcome data will focus on the following variables:

- a) Successful recruitment strategy i.e. recruitment of 64 eligible participants
- b) Data collection on questionnaire and direct assessments for all participants at each assessment time point
- c) Utility of the App and body-worn cameras and quality of data obtained from this equipment.
- d) Retention of families in both groups,
- e) Number of home-based sessions delivered by the therapist
- f) Evaluation of the PECS stages established for treatment families (parent treatment fidelity)
- g) Child and Adolescent Service Use Schedule (CA-SUS) to ascertain local provision
- h) Parent, teacher, research assistant and therapist feedback on feasibility and acceptability (Social Validity Questionnaire, focus groups).

The secondary outcome data will focus on the following:

a) PECS usage - (telephone App and video). The RA will extract frequency counts from the App and score episodes of requesting from films (remaining blind to group allocation).

Experience of coding behaviour from video suggests that it should be possible to scroll through the video at a medium-fast forward pace to identify episodes of requesting behaviour and then to score them according to 2 codes: 1) use of PECS, 2) other forms of request (e.g. speech, vocalisations or gestures etc.)

b) Communication Development Inventory (CDI) to explore whether there has been any overall change in children's communication skills.

Additional outcome data:

a) A short anonymous questionnaire to explore children's access to PECS intervention from professionals working with children with autism. The questionnaire will be circulated through professional Clinical Excellent Networks (CENs) via Survey Monkey. It is designed to take under 10 minutes to complete, consisting mainly of multiple choice questions.

b) A short anonymous questionnaire to ascertain if individuals transferring to adult services do so with some skills using PECS and also to establish if PECS is included in treatment for adults. The questionnaire will be sent through professional Clinical Excellence Networks (CENs) to professionals working in adult therapy services via Survey Monkey. It takes under 10 minutes to complete and is mainly comprised of multiple choice questions.

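### The CDI is described only as a comparison of change, while the other secondary outcome is adjusted for baseline and school; giving the CDI the same adjustment costs one sentence and essentially no precision

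*Protocol*

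**What the plan says.** Section 8 of the Protocol lists two secondary outcomes: PECS usage from the App and video, and the CDI. The CDI is there "to explore whether there has been any overall change in children's communication skills".

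Section 9 treats them differently. The request counts are analysed by intention to treat in a mixed ANOVA, "accounting for clustering within school and covarying for baseline score on the same measure". The CDI gets one sentence: "Change in vocabulary use (assessed by the CDI) will also be compared across groups". It names no model, covariate, school term or analysis population.

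A baseline CDI value will exist. The table of assessment measures puts the CDI among those taken both pre and post treatment. Section 6.1 gives the scale ("Raw scores will be used to assess the understanding and use of vocabulary and nonverbal gestural signals") and the repeat use ("It will also be used at the end of intervention to explore whether there has been any overall change in children's communication skills").

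Two further facts bear on the point. Section 5.3 randomises in blocks of 16 within school. Section 5.2 limits entry to children described as "Non/minimally verbal (i.e. fewer than 10 words used on a regular basis".

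**The concern.** Within one paragraph, baseline and school are written in for one secondary outcome and absent for the other, where change is named as the quantity compared. Taken literally, that is a difference in mean change between groups.

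An unadjusted change score fixes the coefficient on baseline at 1 instead of estimating it. Whenever the true slope of post on baseline differs from 1, two things follow. The between-group estimate has a larger variance than it needs. In addition, given a chance baseline difference between the groups, the estimate is displaced by an amount that baseline adjustment would remove.

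Aim (e) in section 5.1 is to supply pilot data, including effect size, for a larger trial. A CDI estimate on a different footing from the request outcomes is harder to set beside them and may be less precise.

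**Working it through.** **The plan's own figure.** No power is stated for the CDI. The stated power, for the rate of PECS requests, is 47% at an effect size of 0.5 and 62% at 0.6, two-sided 0.05, with 10% loss from 32 per arm. This leaves 32 × 0.9 = 28.8 per arm. Under the normal approximation:

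- d=0.5: 0.5×√(28.8/2) − 1.96 = 1.897 − 1.96 = −0.063, giving 47.5%.
- d=0.6: 0.6×√(28.8/2) − 1.96 = 2.277 − 1.96 = 0.317, giving 62.4%.

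The figures reproduce (a t-test gives 46.2% and 60.9%). They use no baseline covariate and no allowance for clustering, and they do not concern the CDI. Below, 28.8 per arm is used only as a convenient sample size.

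**Variance comparison.** Let baseline SD = 1, post SD = k and baseline-post correlation = r, with a common linear slope rk in both arms. Per child:

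- unadjusted change: k² + 1 − 2rk
- baseline-adjusted: k²(1 − r²)
- difference: 1 − 2rk + r²k² = (1 − rk)², which is never negative
- ratio, adjusted/change: k²(1 − r²)/(k² + 1 − 2rk), which reduces to (1 + r)/2 when k = 1

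The Protocol gives neither r nor k for the CDI, so both are assumed over a range:

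| r | k = 1 | k = 1.5 |
|---|---|---|
| 0.3 | 0.65 | 2.0475/2.35 = 0.87 |
| 0.5 | 0.75 | 1.6875/1.75 = 0.96 |
| 0.7 | 0.85 | 1.1475/1.15 = 0.998 |
| 0.9 | 0.95 | 0.4275/0.55 = 0.78 |

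On 57.6 analysed children with k = 1, the change score gives up the equivalent of 57.6 × (1 − ratio): about 20, 14, 9 and 3 children at r = 0.3, 0.5, 0.7 and 0.9.

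**Power, for illustration.** For a difference of 0.5 post-score SD with k = 1 (noncentral t, 28.8 per arm), change score against adjusted:

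- r = 0.3: 35% against 50%
- r = 0.5: 46% against 58%
- r = 0.7: 67% against 74%
- r = 0.9: 98.6% against 99.0%

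**Chance imbalance.** Given an observed baseline difference D, the change-score estimate is displaced by −(1 − rk)D. At 32 per arm, one standard error of D is √(2/32) = 0.25 baseline SD.

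- k = 1, r = 0.5 (slope 0.5): 0.5 × 0.25 = 0.125 SD, against the imbalance.
- k = 1.5, r = 0.7 (slope 1.05): 0.05 × 0.25 = 0.0125 SD, in the direction of the imbalance.

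The sign therefore depends on whether rk is below or above 1. Averaged over randomisations the change score is unbiased.

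**Price of adjusting.** One degree of freedom goes to baseline. If school is fitted as a fixed effect, three more go to the 64/16 = 4 schools that the block size implies. The two-group comparison has about 57.6 − 2 = 55.6.

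**The case against.** The strongest reply is that the sentence says what is compared, not how. The word *also* may carry over the model described earlier in the same paragraph. Change with baseline CDI as covariate gives exactly the same treatment estimate as the baseline-adjusted post score, so naming change does not exclude adjustment. Covariates for a secondary outcome are often left to a statistical analysis plan, which is not shown here. This stands. A reader might infer that the plan commits to an unadjusted analysis and discards the school structure, but the Protocol states neither.

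A reader might also infer that the entry limit on words makes the correlation modest and the loss therefore large. The Protocol does not establish this. The limit could lower r, but by compressing baseline spread it could also raise k, and at k = 1.5 the loss nearly vanishes for r of 0.5 to 0.7. Section 4 reports that minimally verbal children of school age make hardly any progress in vocal output over a year at school. That is some reason to expect stable scores, though an absence of average gain is not itself a correlation. Nor can the direction of any displacement be stated in advance.

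Finally, the trial is a feasibility study whose primary outcomes are recruitment, data collection, retention, delivery and acceptability. This limits the consequence. It does not remove the case for the change: a baseline is already collected, the adjusted analysis is at least as precise apart from a few degrees of freedom, and the wording differs without any reason given.

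**Conclusion.** The point holds as a minor one. Section 9 states baseline and school adjustment for the request outcomes and states neither for the CDI. If the CDI is analysed as an unadjusted change score, the variance that adjustment would save runs from almost nil (0.2% at k = 1.5, r = 0.7) to about a third (35% at k = 1, r = 0.3). The direction of the comparison is certain, because (1 − rk)² cannot be negative. Its size is not, because it rests on assumed values of r and k and on a common linear slope. The sample-size equivalents also assume the planned 64 with 10% loss. The COVID-19 appendices report that recruitment closed early and do not give a final number.

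Severity is low. The CDI is exploratory, and no stated sample size or power depends on it.

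**What to change.** Replace the CDI sentence in section 9 with: *Post-treatment CDI raw vocabulary scores will be compared between groups by intention to treat in the same model as the request outcomes, with baseline CDI score as covariate and school accounted for.*

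If adjusted change was intended all along, this leaves the treatment estimate unchanged and makes the intention plain. The cost is one sentence and a few degrees of freedom. No further data are needed.

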#### **10. TIMESCALE FOR THE PROJECT**

The duration of the project will be 32 months. The expected completion date of the project is 10/12/2021.

#### **11. COSTING FOR THE PROJECT**

	Year 1	Year 2	Year 3	Total
Staff				
	£86,523	£72,103	£14,421	£173,046
		-		
Materials				
	£2,571			£2,571
Equipment				
	£3,163	£480		£3,643
Travel				
	£4,567	£4,217		£8,784
Other expenses				
	£3,000		£6,060	£9,060
TOTAL	£99,824	£76,800	£20,481	£197,104

#### **12. ETHICS AND REGULATORY APPROVALS**

#### Ethical approval

The sponsor site is Evelina Children's Hospital (GSTT) but the participants will be volunteers (parents) recruited through schools. We will approach the senior management teams or relevant individuals with ethical oversight at participating schools. The R&D department of Evelina Children's Hospital (GSTT NHS Foundation Trust) have reviewed the application, provided research costings and advised the researchers that NHS ethical approval is not required for this study. However, we will seek KCL and local R&D approval.

#### Data handling and confidentiality

Data will be processed in accordance with the General Data Protection Regulation 2016 (GDPR). All research data is stored separate from personal data, using a unique code. Any information shared with third parties will be anonymised. No video or audio data will be used without consent. All information which is collected during the research will be kept strictly confidential as follows:

a) Paper assessments such as questionnaires, contact details, consent forms and correspondence with families and schools. These will stored in such a way as to keep study identity numbers and personal details (i.e. contact details) separately. These papers will be collected from parents or school staff in person unless there is agreement for them to be posted or sent by encrypted email to the study team. We will store all therapy related papers in a locked cabinet in a secure location at the Evelina Children's Hospital (Becket House) and research documents at the Institute of Psychiatry, Psychology & Neuroscience (IOPPN) (Henry Wellcome Building).

- b) The tally counts from parents' mobile phones will be easily downloaded by parents and send to a nominated member of our research staff via encrypted email. These data will be stored on an encrypted external hard drive by a designated member of the research team.
- c) Video recordings from the camera will be downloaded and stored in an external encrypted hard drive by a member of the research team. Only authorised members of the research team will have access to this data.
- d) Computer files will be stored on devices that are encrypted (protected) and kept separately in password protected storage.
- e) No identifying information will appear on any other reports or presentations produced by the study team. For further educational use of these video clips, for example for research dissemination, participants will be contacted and consented in all cases.

## Data Protection Statement

The data controllers for this project will be Evelina Children's Hospital (Guy's and St Thomas' NHS Trust and King's College London (KCL). Personal data will be processed for the purpose of the research outlined above. The legal basis for processing personal data for research purposes under GDPR is a 'task in the public interest' Participants will provide consent for the use of your personal data in this study by completing the study consent form.

# **13. PUBLICATION**

The results of the research will be targeted for publication in peer-reviewed journals of general and special interest. The study will also be disseminated in collaboration with [name] and [name] at the National Autistic Society (NAS), will focus on three stakeholder audiences: (1) health practitioners, education professionals and researchers, (2) autistic people and their families, and (3) study participants. We aim to ensure that all three groups are fully informed about the project.

# **15. APPENDICES**

## **15.1 COVID-19 PROTOCOL DEVIATION 1**

## a) Study timeline

- $\circ$  The study activities have been paused since Friday 3rd April 2020.
- A total of 33 families have been recruited so far from three schools. Details of the assessments and the therapy delivery for each group of families are as follows:

Group of families	Assessments	Therapy
School 1	Completed	Completed
School 2	Partially completed (post & follow-up assessments)	Not completed
School 3	Completed (baseline assessments)	Aim to be delivered at a delayed date (i.e. during the summer)

• A fourth school has already agreed to take part in the study. Recruitment for this school is aim to be completed during the autumn.

## b) Letters to parents and schools

Letters will be sent to all participating parents and schools to let them know that the study has been paused during the period of 'lock down' and that the study activities (including recruitment and delivery of therapy) will be resumed as soon as we will be able to.

## 15.2 COVID-19 PROTOCOL DEVIATION 2

## a) Recruitment

• Due to the lock-down regulations and the high demand on NHS staff, recruitment of new participants had to cease on 12/01/2021.

- Four new schools were approached by the study team at the end of 2020. Schools have sent invitation letters to families and the study team has received expressions of interest from families. We did not progress to obtaining consent from the families.
- The study team will write to families who expressed an interest in taking part in the study to explain the circumstances in which we need to close recruitment.
- The study team will contact the four new schools to inform them about the recruitment cessation and will ask them to provide information on how many letters they sent out and how many expressions of interest they received.

# b) Assessments for families already participating in the study (end-point and follow-up assessments)

- Three of the assessments were conducted virtually via Microsoft Teams between 09/12/2020 and 12/01/2021.
- Since 12/01/2021 all the assessments have been conducted virtually via Microsoft Teams.
- The content and structure of the assessments remain the same. The blank equipment and blank forms are sent to parents via post. No identifying information appears on any of the forms.

# c) Therapy sessions

- Three of the weekly sessions were conducted virtually via Microsoft Teams between 03/11/2020 and 12/01/2021.
- Twenty of the fortnightly sessions were conducted virtually via Microsoft Teams between 03/11/2020 and 12/01/2021.
- Since 12/01/2021 all the assessments have been conducted virtually via Microsoft Teams.
- The content and structure of the assessments remain the same. The visual materials are sent to parents via post. No identifying information appears on any of the forms.
